By my signature below, I agree to conduct this Study in accordance with the Clinical Trial Protocol, current Good Clinical Practice (cGCP) and Good Laboratory Practice (cGLP) guidelines, obligations as set forth in Title 21 CFR Parts 812, 54, 5,6 and 11 (as applicable), and any applicable regulatory laws. I will make no changes to protocol-defined procedures without written permission from the Sponsor.

I understand that Investigational Use Products may be used **only** for the purposes explicitly described in this protocol.

I further agree to treat the results of this Study as confidential information and will not submit the results of the Study for publication without prior written authorization from the Sponsor.

[name]

PRINTED NAME

SIGNATURE

7/15/2021

DATE

SYNOPSIS

Title of Study	Phase I study to examine the safety and efficacy of allogeneic MSCs in suppressing inflammation in patients with small abdominal aortic aneurysm (AAA)
Objectives	Assess the safety and efficacy of systemic (IV) administration of escalating doses of allogeneic MSCs in modulating immune cell phenotypes and suppressing aortic inflammation in patients with small AAA.
Planned Number of Subjects and Duration of Involvement	36 patients
Patient Population	Abdominal aortic aneurysms (AAA) patients
Investigational Product Name	Allogeneic mesenchymal stem cells
Methodology Overview	In a double blind, Phase I trial, 36 patients with AAA measuring 30-50mm in maximal transverse diameter (MTD) will be randomized in a 1:1:1 fashion to receive either 1.0×10^6 MSCs/kg (n=12), 3.0×10^6 MSCs/kg. (n=12), or placebo (Plasmalyte A) (n=12) delivered intravenously. The primary safety endpoints will be incidence of treatment related adverse events at 24 months post MSC-administration. Exploratory primary efficacy endpoints will be changes in circulating inflammatory cell phenotypes and aortic inflammation as measured by CT. The treatment period will involve long-term follow-up through 5 years. The incidence of surgical intervention, aneurysm related death, quality of life, and major adverse cardiac events will be recorded.

Table 1 Abbreviations

AAA	Abdominal Aortic Aneurysm
AE	Adverse Event
AMI	Acute Myocardial Infarction
ASC	Adipose derived MSC
bMSC	Bone marrow derived MSC
CTSI	Clinical and Translational Sciences Institute
DSMB	Data Safety Monitoring Board
eGFR	Effective Glomerular Filtration Rate
GVHD	Graft Versus Host Disease
IFN- γ	Interferon- γ ,
IL	Interleukin

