3.3 Proposed Intended Use Statement

Allogeneic MSCs are a novel therapeutic option to suppress growth of small AAA. Human MSCs are intended for investigational use only by selected investigators familiar with their use and experienced in conducting clinical studies. Human MSCs may only be administered to human subjects participating in clinical studies sponsored/approved by Indiana University School of Medicine, and who have provided formal written consent.

3.4 Study Objectives.

The principal objective of this study is as follows:

Assess the safety and efficacy of administration of allogeneic MSCs in patients with small AAA.

This study will test the hypothesis that administration of MSCs in doses of 1×10^6 MSCs/kg. and 3×10^6 MSCs/kg demonstrate safety in patients with small AAA. This trial will also test the hypothesis that MSCs, in a dose dependent fashion (1×10^6 MSC/kg. vs. 3.0×10^6 MSC/kg.), promote the frequency and immune suppressor function of Treg cells and decrease AAA inflammation as measured by computed tomography. In an double blinded, Phase I trial, 36 patients with AAA measuring 35-50 mm in maximal transverse diameter (MTD) will be randomized in a 1:1:1 fashion to receive intra-venously either a single dose of 1×10^6 MSCs/kg., 3×10^6 MSCs/kg. , or placebo (Plasmalyte A) (n =12/group). The primary safety endpoints will be incidence of treatment related adverse events accrued over 24 months. Efficacy measures are changes in frequency and immune suppressor function of Tregs, number and cytotoxic activity of CD4+/CD8+ CD28- T-cells, activated monocytes, and changes in aortic inflammation as measured by PET CT compared to baseline. Secondary endpoints measured out to year 5 will include changes in IL-10 and Tr1 levels. Duplex ultrasound measurements of the AAA, which is considered standard of care, will be recorded as change in aortic inflammation during long-term follow-up. Incidence of surgical intervention, aneurysm related death, quality of life, and major adverse cardiac events will be recorded through year five (5).

Completion of this study will determine if MSCs are safe in patients with AAA and provide critical insights that will direct a placebo-controlled, Phase II randomized trial.

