4.3 Study Duration

It is expected that the study will be completed within 8 years. Each patient will be followed for 24 months for assessment of safety with long-term follow-up through year 5 after enrollment.

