9. STATISTICAL METHODS

The safety of systemic administration of allogeneic MSCs will be measured by treatment-related adverse events. Treatment-related adverse events will be categorized by overlapping systems and severities. The three categories of systems are cardiovascular, respiratory, or infectious. Two categories of severity will be serious adverse (SAE) and major adverse cardiac events (MACE). For completeness, instances of adverse events may appear in more than one category. Within each of these categories adverse events will be listed in descending order of frequency for the treatment-group. In addition, for each category, the sum and difference between the two routes of delivery of the proportions will be reported as percent incidence. Confidence Intervals at the 95% confidence level and *P*-values for these four groups will be calculated. Since four previous trials have not reported adverse events with MSC treatment, confidence intervals will be generated by the method of the Wilson Score Interval because they are robust, with good coverage probability even for small number of trials and are not degenerate near zero. These intervals will be used to summarize the data rather than as any formal inferential statement. No adjustment for multiplicity will be made.

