10. ADVERSE EVENT REPORTING

10.1 Adverse Events and Stopping Rules

Adverse events occurring during the enrollment period should be documented by the Investigator in progress notes, but will not be collected or analyzed by Indiana University School of Medicine unless considered serious by the Investigator. Adverse events will be reported according to federal guidelines for safety reporting for Investigational New Drug Application (IND).

Serious adverse events (SAEs) encountered during study enrollment will be documented by the Investigator and reported to Indiana University School of Medicine immediately upon discovery. SAEs are defined under current Good Clinical Practice (cGCP) guidelines as events that result in one or more of the following:

- life-threatening illness or injury;
- permanent impairment of a body structure or a body function;
- medically necessary in-patient hospitalization;
- medical or surgical intervention necessary to prevent permanent impairment to body structure or function; or
- fetal distress, fetal death, or congenital abnormality.

Serious events that affect the rights, safety, or welfare of subjects must be documented on a form and be reported immediately to Indiana University School of Medicine and to the Investigator’s IRB according to that IRB’s policies.

Major Adverse Cardiac Events (MACE). MACE endpoints will include: death, nonfatal myocardial infarction, including, Q-wave, non Q-wave, and CK/CKMB elevation, stroke, transient ischemic attack (TIA), hospitalization for heart failure, hospitalization for hypo or hypertension, life-threatening arrhythmia, and aneurysm rupture, which will be collected throughout the 6-month time period.

Severity Assessment. We will use the Common Terminology Criteria for Adverse Events (CTCAE), version 4.0, for detailed descriptions of Severity Grades. The CTCAE schema is classified by body system and event using the MedDRA hierarchy and provides descriptions of events that qualify under each severity rating.

The following table contains general descriptions of Adverse Event Severity Grades.

Severity Grade	Description
1	Mild. Asymptomatic or mild symptoms; clinical or diagnostic observations only; intervention is not indicated.
2	Moderate. Minimal, local, or non-invasive intervention indicated or limiting activities of daily living (i.e. preparing meals, shopping for groceries/clothes, managing money, using telephone, etc.)

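### The MACE window is stated as an undefined 6 months in section 10.1 and as five years in section 3.4, with a 24-month safety endpoint between them; one collection and reporting window is needed

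*Combined protocol and SAP*

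**What the plan says.** Section 10.1 is the only place that lists the MACE components. It closes the list with "life-threatening arrhythmia, and aneurysm rupture, which will be collected throughout the 6-month time period".

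Section 3.4 gives a different window for the same outcome: "aneurysm related death, quality of life, and major adverse cardiac events will be recorded through year five (5". The Synopsis agrees in substance. Directly after stating that follow-up runs through 5 years, it says "The incidence of surgical intervention, aneurysm related death, quality of life, and major adverse cardiac events will be recorded".

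A third horizon belongs to safety. The Synopsis says "The primary safety endpoints will be incidence of treatment related adverse events at 24 months post MSC-administration", section 3.4 also gives 24 months, and section 4.3 says "Each patient will be followed for 24 months for assessment of safety with long-term follow-up through year 5 after enrollment". Section 9 brings MACE under that endpoint by classifying treatment-related adverse events: "Two categories of severity will be serious adverse (SAE) and major adverse cardiac events (MACE". It states no time window. It also allows that "instances of adverse events may appear in more than one category".

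Tables 2 and 3 schedule AE/SAE evaluation at every visit to Month 60 but have no MACE row. Section 10.1 opens by saying that adverse events in the enrollment period go into progress notes and are neither collected nor analysed by the sponsor unless the investigator considers them serious.

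**The concern.** One named safety outcome has two explicit collection windows and, through section 9, a third reporting horizon. Staff who apply the definition meet the 6-month limit in the same sentence. Staff who work from the objectives record for five years. The two could report different MACE counts from the same patients, and a published incidence would not show which window it covers.

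The starting point is also open. Section 10.1 gives none, the Synopsis counts from MSC administration, and section 4.3 counts from enrollment. Table 2 places randomization at Baseline and infusion at Day 0, so there is an interval between them. Section 6.1.4 foresees that a MACE could occur just before the planned infusion.

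**Working it through.** There is no stated figure to reproduce, so this is a comparison of text.

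**1. The windows side by side**

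| Place | Window | Start | Events covered |
|---|---|---|---|
| 10.1 | 6 months | not given | MACE |
| Synopsis (safety endpoint) | 24 months | MSC administration | treatment-related adverse events; MACE enters through section 9 |
| 4.3 | 24 months for safety, then to year 5 | enrollment | general follow-up |
| 3.4 | through year 5 | not given | MACE, related or not |
| Section 9 | none given | none given | MACE as a category of treatment-related events |

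**2. Does another section define the 6 months?** The other 6-month references are the AAA-expansion stopping rule, the Month 6 visit, the 6-month antibody sample and the six-monthly follow-up interval. None of them is a MACE window. Two front parts of the document and one part after the stopping rules were not available, so this holds for the available text. The conflict between 10.1 and 3.4 stands either way.

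**3. Size of the difference.** 6/24 = 25% of the safety horizon. 6/60 = 10% of the five-year record.

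**4. Which late events depend on the window?** The SAE list in 10.1 includes life-threatening illness and medically necessary hospitalisation. Hospitalisation for heart failure and life-threatening arrhythmia meet it by definition, and most infarctions, strokes and ruptures would ordinarily meet it too. These reach the record through the AE/SAE row at any visit to Month 60 and can also be tabulated as MACE, since section 9 lets categories overlap. A TIA is a listed component ("and CK/CKMB elevation, stroke, transient ischemic attack (TIA"), and one managed without admission need not meet the SAE list.

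**5. Could the AE/SAE row pick up a non-serious late TIA?** Possibly not, because of the opening sentence of 10.1. The enrollment period is not defined there. If it means accrual, which section 5.2.2 puts at about 1–2 years, then the exclusion ends about 24 months after the first patient enters. It can reach at most the Month 12, 18 and 24 visits, and only for patients enrolled early. Visits at Months 30 to 60 fall outside it.

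**6. What one event does.** The plan uses 95% Wilson intervals with 12 patients per arm.

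- 0/12: upper limit = z²/(n + z²) = 3.84/15.84 = 24.2%, so 0 to 24.2%.
- 1/12: centre = (1/12 + 3.84/24)/(1 + 3.84/12) = 0.184 and half-width = 0.170, so 8.3% with interval 1.5% to 35.4%.

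This change reaches the 24-month summary only if the event is late, left out and judged treatment-related. The five-year record in 3.4 does not require relatedness.

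**The case against.** The strongest reply is that little is lost. Section 10.1 does not forbid later collection, AE/SAE evaluation continues to Month 60, and most MACE would be SAEs. No stopping rule uses the composite. Section 9 says its intervals summarise the data and are not formal inference. All of this stands, and it limits the size of the point. It does not settle which window a reported incidence covers, and it does not secure late events that are not serious.

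Four stronger readings are tempting, and the documents do not support them.

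- **All MACE after Month 6 are lost.** They are not; the AE/SAE row would capture most of them.
- **Isolated CK/CKMB elevations are an exposed component.** Section 10.1 lists enzyme elevation with Q-wave and non Q-wave under nonfatal myocardial infarction, so it is not plainly a component of its own.
- **The exclusion of non-serious events removes late MACE throughout long-term follow-up.** On the accrual reading it stops at about Month 24, and it affects early enrollees only.
- **Stopping is compromised because rupture is a MACE component and one rule counts ruptures over 12 months.** That rule counts ruptures directly, and a rupture would be reported as an SAE whatever the MACE window.

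**Conclusion.** The inconsistency is real and should be corrected. MACE incidence can be read as a 6-, 24- or 60-month quantity, and the shortest window covers 25% and 10% of the other two. The effect on capture is narrow: late MACE that need not be serious, with the non-hospitalised TIA as the clear example. The effect on reporting is broader, because the window stays ambiguous even if every event is captured. The five-year record takes in all MACE, while the 24-month summary takes in only those judged treatment-related.

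The documents give no MACE rate, so the number of events affected cannot be estimated. The conclusion assumes that the unavailable parts do not define the 6-month period. It also takes section 9 at its word that MACE is a category of the 24-month safety endpoint. The point concerns the clarity and completeness of the safety record, not a formal test or a stopping decision.

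**What to change.** Reconcile 10.1 with 3.4 and 4.3.

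1. In 10.1, replace the 6-month phrase with collection through Month 60, and state that MACE incidence is also summarised at Month 24 to match the safety endpoint.
2. State the start point. Collect from randomization and flag events before infusion separately, so that the post-infusion summary runs from Day 0. Starting collection at Day 0 would omit a MACE in a randomised patient before infusion.
3. Except MACE from the opening sentence of 10.1, so that MACE are collected and analysed whether or not they are serious. Without this, a table footnote alone could contradict that sentence.
4. Add a matching footnote to the AE/SAE rows of Tables 2 and 3: includes MACE as listed in 10.1, serious or not.

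The cost is a few sentences in 10.1 and one footnote in two tables. The small downside is recording a few non-serious MACE at visits already scheduled. No visit, test or stopping rule changes.

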11. RISK ANALYSIS

11.1 Potential Risks of the Investigational Product and Clinical Investigation

Study sites will not be provided with an investigational device.

The types of risk associated with injection of allogeneic MSCs align with those associated with injection of autologous bone marrow mononuclear cells (ABMNCs), most notably rash, mild fever, and myalgia. These risks are mild and rare. These risks are all stated in the consent form.

11.2 Potential Benefits of the Investigational Product and Clinical Investigation

Subjects are not expected to benefit in any way from their participation in the study.

The studies made possible by the data collected in this study are expected to lead to effective therapeutic strategies using MSCs or their secreted products to suppress expansion of small AAA negating the need for surgery and preventing rupture.

11.3 Minimization of Risks

Although the risk to subjects participating in the study is anticipated to be minimal, the clinician, at his/her discretion, will not collect data from those individuals for whom collection is judged to pose an unusually high risk of physical or mental harm or discomfort. Participation in this study poses no risk to study personnel other than that normally encountered during standard practice. These risks will be minimized by adherence to the following guidelines:

- Personnel should wear appropriate personal protective equipment to avoid contact of the eyes or skin with hazardous materials or products derived from biological sources.

12. INVESTIGATOR RESPONSIBILITIES

12.1 Site Qualification and Study Oversight

The PI is responsible for general administration of the study.

Before the study, the PI must:

- Obtain approval to conduct the study from the study site's IRB;
- Sign the Signature Page him/herself and have all sub-investigators sign the Signature Page and return it to Indiana University School of Medicine;
- Provide financial disclosures to Indiana University School of Medicine for themselves and all sub-investigators participating in study conduct, per Title 21CFR 54 (see **Section 12.4** below).

During the study, the PI must ensure that:

- The study is conducted ethically;
- Case report forms (CRFs), including Subject ICFs, are provided with each transfer of data requiring informed consent; and
- All other study forms are completed as instructed by Indiana University School of Medicine.

In the case of completion or termination of the study or an Investigator's role in the study, or at Indiana University School of Medicine request, all study materials must be returned to Indiana University School of Medicine.

12.2 Case Report Forms/Electronic Data Records

As used in this protocol, the term CRF should be understood to refer to either a paper form or an electronic data record or both, depending on the data collection method(s) used.

Original CRFs are the sole property of Indiana University School of Medicine and should not be made available in any form to third parties, except for authorized representatives of Indiana University School of Medicine or appropriate regulatory authorities, without written permission from Indiana University School of Medicine.

It is the PI's responsibility to ensure completion, review, and approval of all CRFs. CRFs must be signed by the PI or by an authorized staff member. These signatures serve to attest that the information contained on the CRFs is true. At all times, the PI has final personal responsibility for the accuracy and authenticity of all clinical and laboratory data entered on the CRFs.

12.3 Access to Source Documents

Indiana University School of Medicine or its agents and appropriate regulatory authorities shall be granted direct access to all study-related documents to perform verification that the protocol and all applicable current Good Laboratory Practices (cGLPs), Good Clinical Practices (GCPs), and regulations are being followed and to confirm that study documents are complete and accurate. It is important that Investigator(s) and their relevant personnel be made available during monitoring visits and any audits or inspections, and that sufficient time is allotted for the process.

12.4 Financial Disclosure

Investigators must provide Indiana University School of Medicine with sufficient, accurate financial information in accordance with local regulations to allow Indiana University School of Medicine to submit complete and accurate financial certification or disclosure statements to the appropriate health authorities. Investigators are responsible for providing information to Indiana University School of Medicine concerning their relevant financial interests during the course of the study and for 1 year after completion of the study. Conflicts of interest should be disclosed as required by law.

Financial support for this project is provided by Indiana Clinical and Translational Sciences Institute (CTSI).

12.5 Deviations from the Study Protocol

An Investigator may not deviate from the study protocol without prior approval by Indiana University School of Medicine unless the deviations are necessary under emergency circumstances to protect the rights, safety, or well-being of human subjects or the scientific integrity of the clinical investigation. These deviations must be documented and promptly reported to Indiana University School of Medicine and, if applicable, to the IRB providing oversight of the study. Protocol deviations may result in corrective and preventive actions and/or disqualification of the Investigator.

12.6 Record Retention

To enable evaluations and/or audits from regulatory authorities or Indiana University School of Medicine, the PI and all sub-investigators agrees to retain all study records, including copies of all CRFs, UADE forms, and source documents, for 3 years following completion of the project dependent upon the study data. The Investigator must obtain the Indiana University School of Medicine written permission before disposing of any records, even if retention requirements have been met.

If an Investigator relocates, retires, or for any other reason withdraws from the trial, Indiana University School of Medicine must be notified in advance, and study records must be transferred to a designee acceptable to Indiana University School of Medicine. This designee might be another Investigator, another institution, or Indiana University School of Medicine itself.

12.7 Publication Policy

The results of this study will be submitted for publication to a medical journal. The PI agrees that any publication of data from this study will comply with Indiana University School of Medicine publication policy, the instructions to authors outlined by the editor of the journal or conference proceedings where the data is to be published, and the spirit of recommendations made in the good publication practice guidelines (GPP2) of the International Society of Medical Publication Professionals. Indiana University School of Medicine has the right to review any manuscripts, presentations, or abstracts that originate from this study or that utilize these data before they are submitted for publication or other means of communication.

